2.3.2 Rituximab and chlorambucil

Rituximab in combination with chlorambucil is one of the preferred regimens per Chinese CLL/SLL Diagnostic and Treatment Guideline ([Version 2018](#)) for medically unfit CLL patients. Risks associated with rituximab and chlorambucil are described in the local prescribing information (i.e., Summary of Product Characteristics, etc).

Overall, the available clinical data including the safety experience support further clinical investigation of acalabrutinib as well as rituximab in combination with chlorambucil in this study. Precautionary safety measures, and regular monitoring of safety by the sponsor enable early identification of safety signals in the study and minimize the risk to subjects.

In conclusion, it is considered that the benefit risk ratio for this study is favorable.

3 OBJECTIVES AND ENDPOINTS

Table 4 Study Objectives

Primary objective:	Endpoint/variable:
To compare the efficacy of acalabrutinib relative to chlorambucil plus rituximab in subjects with previously untreated chronic lymphocytic leukemia without del(17p) or TP53 mutation	Progression free survival is defined as time from randomization until progression per the International Workshop on Chronic Lymphocytic Leukemia 2018 criteria as assessed by blinded independent central review or death due to any cause
Secondary objectives:	Endpoints/variables:
To compare acalabrutinib relative to chlorambucil plus rituximab on overall response rate, duration of response, time to next treatment, and overall survival	
 • Overall response rate is defined as the proportion of patients who have a complete response, complete response with incomplete bone marrow recovery, nodular partial response or partial response, as determined by blinded independent central review and investigator per International Workshop on Chronic Lymphocytic Leukemia 2018 criteria • Duration of response is defined as the time from the date of first documented response until date of documented progression or death in the absence of disease progression, as determined by blinded independent central review and investigator • Time to next therapy is defined as time from randomization until institution of non- protocol specified treatment for chronic lymphocytic leukemia • Overall survival is the length of time from randomization until the date of death due to any cause
To evaluate minimal residual disease negativity rate during treatment and at the end of treatment	Minimal residual disease negativity rate (peripheral blood) at the start of Cycle 9
To characterize the pharmacokinetics of acalabrutinib and its major metabolite (ACP-5862)	Summarized plasma concentrations of acalabrutinib and ACP-5862 at specified time points Pharmacokinetic parameters by population analyses as appropriate

Safety objective:	Endpoints/variables:

To assess the safety and tolerability of acalabrutinib as compared to chlorambucil plus rituximab in subjects with previously untreated chronic lymphocytic leukemia without del(17p) or TP53 mutation
	
Safety and tolerability will be evaluated in terms of adverse events, vital signs, clinical laboratory, physical examinations, and electrocardiogram
 
Assessments related to adverse events cover
 
 • Occurrence/frequency • Relationship to investigational product as assessed by investigator • Common Terminology Criteria for Adverse Events severity grade • Seriousness • Death • Adverse events leading to discontinuation of investigational product • Adverse events leading to dose reduction of investigational product • Adverse events leading to dose delay of investigational product 
Vital signs parameters include systolic and diastolic blood pressure, and pulse rate, body temperature.
 
Assessments cover
 
 • Observed value • Absolute change from baseline values over time
Exploratory objectives:	Endpoint/variable:

CCI
	

Note: Sensitivity analysis of PFS will be performed based on the investigator's assessment according to IWCLL 2018.

4 Study DESIGN

4.1 Overall design

This randomized, regional, multicenter, open-label, Phase 3 study will evaluate the efficacy and safety of acalabrutinib monotherapy versus chlorambucil plus rituximab in subjects with previously untreated CLL without del(17p) or TP53 mutation.

Approximately 150 subjects will be randomized in a 1:1 ratio into 2 treatment arms (n=75 subjects each) to receive either acalabrutinib monotherapy (Arm A) or rituximab in combination with chlorambucil (Arm B). It is planned to randomize approximately 75 to 120 patients in total (50% to 80% of total sample size) from China. Randomization will be stratified by ECOG [0-1 versus 2] and Rai stage [0-II versus III-IV]. A schedule of screening and trial assessments is provided in [Table 1](#) (Arm A) and [Table 2](#) (Arm B).

At investigator discretion, subjects randomized to Arm B who have BICR-confirmed or investigator-assessed (after FA and per Amendment 5.0) disease progression and meet eligibility for crossover are permitted to receive acalabrutinib monotherapy treatment until disease progression or unacceptable toxicity. For the details, please refer to [Section 6.8](#).

Subject participation will include a screening phase, treatment phase, post-treatment disease follow-up phase, and survival follow-up phase. The screening phase will last up to 28 days before the first dose of study drug, during which the subject's eligibility and baseline characteristics will be determined. The treatment phase will last from randomization until study drug(s) discontinuation. Treatment with acalabrutinib may be continued until disease progression or any other treatment discontinuation criterion is met. Treatment with chlorambucil/rituximab is up to 6 cycles, or until there is disease progression or any other treatment discontinuation criterion is met. Dose modification provisions are provided in [Section 6.6](#).

Assessment for tumor response and progression will be conducted in accordance with the IWCLL 2018 criteria. Disease assessments will be done according to SoA until confirmation of disease progression or death, consent withdrawal, or lost to follow-up. Subjects from Arm B who have BICR-confirmed or investigator-assessed (after FA and per Amendment 5.0) disease progression may be eligible to crossover and receive single agent acalabrutinib 100 mg BID at investigator discretion. An end-of-treatment (EoT) visit is required for safety assessments for any subjects who permanently discontinue study treatment for any reason (except for death, lost to follow-up, or withdrawal of consent), including disease progression. The EoT visit should be performed within 7 days of the last dose of all study drugs, if possible, and is not required for subjects who discontinue from study treatment within 10 days of a scheduled study visit, or if the EoT visit would be performed within 14 days of the safety follow-up (SFU) visit.

The survival follow-up will begin after BICR- or investigator-confirmed progressive disease. During this phase, subsequent anticancer therapy to treat CLL including best response, IWCLL indication for treatment initiation, additional malignancy occurrence, and survival status will be recorded. The survival follow-up will continue until death, lost to follow-up, consent withdrawal, or study closure, whichever occurs first. For treatment after the end of study see Section 6.7.

For an overview of the study design see Figure 1, Section 1.3. For details on treatments given during the study, see Section 6 Study Treatments.

For details on what is included in the efficacy and safety endpoints, see Section 3 Objectives and Endpoints.

4.1.1 Study Conduct Mitigation During Study Disruptions Due to Cases of Civil Crisis, Natural Disaster, or Public Health Crisis

The guidance given below supersedes instructions provided elsewhere in this CSP and should be implemented only during cases of civil crisis, natural disaster, or public health crisis (eg, during quarantines and resulting site closures, regional travel restrictions, and considerations if site personnel or study participants become infected with SARS-CoV-2 or similar pandemic infection) which would prevent the conduct of study-related activities at study sites, thereby compromising the study site staff or the participant's ability to conduct the study. The investigator or designee should contact the study Sponsor to discuss whether the mitigation plans below should be implemented.

To ensure continuity of the clinical study during a civil crisis, natural disaster, or public health crisis, changes may be implemented to ensure the safety of study participants, maintain compliance with Good Clinical Practice, and minimize risks to study integrity.

Where allowable by local health authorities, ethics committees, healthcare provider guidelines (eg, hospital policies) or local government, these changes may include the following options:

- **Rescreening:** Additional rescreening for screen failure and to confirm eligibility to participate in the clinical study can be performed in previously screened participants. The investigator should confirm this with the designated study physician.
- **Home or Remote visit:** Performed by a site qualified Health Care Professional (HCP) or HCP provided by a third-party vendor (TPV).
- **Telemedicine visit:** Remote contact with the participants using telecommunications technology including phone calls, virtual or video visits, and mobile health devices. Home delivery of Acalabrutinib by a designated courier. If a site visit is not possible, Acalabrutinib may be delivered to the participant's home by a designated courier if feasible. The option of home delivery ensures a participant's safety in cases of a pandemic where participants may be at increased risk by travelling to the site/clinic. This will also minimize interruption of Acalabrutinib administration during other study

- disruptions, eg, site closures due to natural disaster.
- At-home Investigational Product (IP) administration: Performed by a site qualified HCP, or by the participants or the participant's caregiver, if possible. Additional information related to the visit can be obtained via telemedicine.
 - Home delivery of Acalabrutinib by a designated courier: If a site visit is not possible, Acalabrutinib may be delivered to the participant's home by a designated courier if feasible. The option of home delivery ensures a participant's safety in cases of a pandemic where participants may be at increased risk by travelling to the site/clinic. This will also minimize interruption of Acalabrutinib administration during other study disruptions, eg, site closures due to natural disaster.

For further details on study conduct during civil crisis, natural disaster, or public health crisis, refer to [Appendix J](#).

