- a. Subjects who stop both drugs early because of an adverse event and disease progression has not occurred at that time, will then enter an Post-treatment disease follow up phase. Post-treatment disease follow-up visits should occur approximately every 12 weeks or 24 weeks from the date of last disease evaluation until disease progression, regardless of whether the subject receives a new anticancer therapy.
- b. An end of treatment visit will be done within 7 days for subjects who permanently discontinue study drugs early for any reason (except for death, lost to follow-up, or withdrawal of consent), including disease progression. See detail in Section 7.1.1. A safety follow-up visit is conducted 30 days (+7 days) after the last dose of study drug, regardless of whether the subject receives a new anticancer therapy or demonstrates disease progression within this timeframe. If the safety follow-up visit is within ± 7 days of a regularly scheduled visit during the Post-treatment Phase, the visits may be combined into a single visit.
- c. Response evaluations will be done every 12 weeks (± 14 days) with the first on-treatment assessment occurring on Cycle 4 Day 1, the second on Cycle 7 Day 1, and so on through Cycle 25. After Cycle 25 response evaluations will be done every 24 weeks (± 14 days) thereafter, until disease progression. For additional details on the confirmatory bone marrow biopsy for subjects in Arm B, see Minimal Residual Disease/Response Evaluation in Section 8.1.2.
- d. Hepatitis serology must include hepatitis B surface antigen (HBsAg/HbsAg), hepatitis B surface antibody (anti-HBs), hepatitis B core antibody (anti-HBc), and hepatitis C (HCV) antibody.
- e. After the end of the protocol-defined adverse event reporting period (Section 8.3.1), only serious adverse events considered related to study drug(s) or study procedures are required to be collected.
- f. Women of childbearing potential only. A urine or serum pregnancy test is acceptable. Pregnancy testing can be done more frequently than the protocol-defined schedule.

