7.1.2 Follow-up for progression and survival

Post-treatment Disease Follow up: All subjects enrolled who complete the study treatment (Arm B) or discontinue from study treatment due to reasons other than disease progression will be followed for disease evaluation approximately every 12 weeks or 24 weeks from the latest date of disease evaluation before study treatment discontinuation until disease progression, regardless of whether the subject receives a new anti-CLL therapy.

Survival Follow up: All subjects who have disease progression and have not withdrawn consent will be contacted approximately every 24 weeks by clinical visit or telephone, to assess survival and the use of alternative anti-CLL therapy and occurrence of any secondary malignancies until death or lost to follow up. At the time of the planned final analysis, a survival sweep may be conducted. All subjects who are on study and not known to have died before the survival sweep may be contacted at that time.

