A central imaging service will be used to provide independent radiologic assessments for the purposes of the primary endpoint. All imaging assessments (including unscheduled visit scan) will be sent to the sponsor appointed central reader on an ongoing basis. Assessment of scans by BICR will be triggered only upon investigator-assessed progression for both arms and the BICR confirmation will be reported back to sites. If the BICR does not confirm disease progression, tumor assessments should be continued in line with the schedule of assessments. Since the primary analysis of the study is based on BICR, it is important that study treatment and scheduled imaging assessments continue until progression confirmed by BICR. After the final analysis and per Amendment 5.0, disease progression can be assessed by investigator.

If at the time of primary PFS analysis it is identified that a patient has disease progression by BICR that has not been identified by the investigator, the sponsor will contact the investigator to discuss whether continued treatment with study medication is appropriate.

The investigator must evaluate the response of the subject per IWCLL criteria (see Table 10).

Table 10 Response Assessment Criteria for CLL (modified from Hallek 2018) – IWCLL Criteria

Group	Parameter	CR a	PR b	PD	SD
A	Lymph nodes	None ≥ 1.5 cm	Decrease $\geq 50\%$ (from baseline) c	Increase $\geq 50\%$ from baseline or from response	Change of -49% to +49%
	Liver and/or spleen size d	Spleen size < 13 cm; liver size normal	Decrease $\geq 50\%$ (from baseline)	Increase $\geq 50\%$ from baseline or from response	Change of -49% to +49%
	Constitutional symptoms	None	Any	Any	Any
	Circulating lymphocyte count	Normal	Decrease $\geq 50\%$ from baseline	Increase $\geq 50\%$ over nadir with absolute count $\geq 5 \times 10^9/L$	Change of -49% to +49%
B	Platelet count	$\geq 100,000/\mu L$	$\geq 100,000/\mu L$ or increase $\geq 50\%$ over baseline	Decrease of $\geq 50\%$ from baseline secondary to CLL	Change of -49% to +49%
	Hemoglobin	≥ 11.0 g/dL (untransfused and without erythropoietin)	≥ 11 g/dL or increase $\geq 50\%$ over baseline	Decrease of ≥ 2 g/dL from baseline secondary to CLL	Increase < 11.0 g/dL or $< 50\%$ over baseline, or decrease > 2 g/dL
	Marrow	Normocellular, no CLL cells, no B-lymphoid nodules	Presence of CLL cells, or of B-lymphoid nodules, or not done	Increase of CLL cells by $\geq 50\%$ on successive biopsies	No change in marrow infiltrate

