## 1. STUDY DETAILS

[figure not shown]
This statistical analysis plan (SAP) contains a more detailed description of the analyses described in the clinical study protocol (CSP) with the exception of analyses described in section 9.5.5, regarding combined PK analyses across different studies. This SAP is based on version 4.0 of the CSP.

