The survival follow-up will begin after BICR or investigator-confirmed progressive disease. During this phase the following information will be recorded: subsequent anti-CLL therapy including best response, IWCLL indication for treatment initiation, additional malignancy occurrence, and survival status. The survival follow-up will continue until death, lost to follow-up, consent withdrawal, or study closure, whichever occurs first.

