#### **PFS sensitivity analyses**

The following sensitivity analyses will be performed:

- In addition to the stratified primary analysis the unstratified log rank test and unstratified hazard ratios will be calculated.
- The primary analysis will also be repeated without PFS censoring to subsequent therapies. Therefore, patients who receive a subsequent therapy prior to progression or death will be assigned an event time according to their recorded progression or death date. Patients who receive a subsequent therapy and did not progress or die will be censored according to the rules in table 4 other than the subsequent therapy rule.

- The primary analysis will be repeated except that the actual PFS event times, rather than the censored times, of patients who progressed or died in the absence of progression immediately following two, or more, tumor assessments will be included. This will be supported by a Kaplan-Meier plot of the time to censoring where the censoring indicator of the primary PFS analysis is reversed (what was originally a censored event in the primary PFS analysis becomes an actual event and what was originally a PFS event becomes a censored event) will be presented.
- Ascertainment bias will be assessed by analyzing the investigator data. The stratified log rank test will be repeated on PFS using the investigator data based upon IWCLL 2018. The HR and CI will be presented.
- Concordance between Investigator and BICR assessed progression will be presented for each treatment group.

If there is an important discrepancy between the primary analysis using the BICR data and this sensitivity analysis using investigator data then the proportion of patients with site confirmation but no central confirmation of progression will be summarized; such patients have the potential to induce bias in the central review due to informative censoring. An approach of imputing an event at the next visit in the central review analysis may help inform the most likely HR value ([Fleischer et al 2011](#)), but only if an important discrepancy exists.

The primary analysis may also be repeated using the randomization strata as entered into the database rather than those entered into the IVRS system, but only if the proportion of patients with a discrepancy is more than 10%.

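### Protocol 4.1 and SAP 1.2 start survival follow-up at BICR or investigator progression, while Protocol 8.1.1 keeps imaging going until BICR confirms it; the mismatch allows informative censoring of the primary endpoint

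*Protocol*

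**What the plan says.** **When survival follow-up starts.** Protocol 4.1: "The survival follow-up will begin after BICR- or investigator-confirmed progressive disease". SAP 1.2: "The survival follow-up will begin after BICR or investigator-confirmed progressive disease". Neither sentence is limited to the period after the final analysis. Protocol 4.1 and 7.1.2 describe the phase as collecting survival status, later CLL therapy and new malignancies. Contact is about every 24 weeks, and a telephone call is enough. In Protocol Tables 2 and 3 the CT and overall-response rows have no entry under survival follow-up. Those rows of Table 1 could not be read in the text available.

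**When imaging ends.** Protocol 8.1.1: "If the BICR does not confirm disease progression, tumor assessments should be continued in line with the schedule of assessments", and "it is important that study treatment and scheduled imaging assessments continue until progression confirmed by BICR". The same section accepts investigator-assessed progression only after the final analysis, under Amendment 5.0. Protocol 7.1.2 and the response-evaluation footnotes to Tables 1 and 2 end assessments at disease progression and do not say whose assessment counts. Protocol 4.1 ends them at confirmation of progression and does not name who confirms.

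**Feedback to sites.** Protocol 8.1.1 has the BICR confirmation reported back to sites. SAP 3.2.6 says that results are not reported back.

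**Censoring.** Under SAP 3.3.1 and Table 4, a patient without documented progression or death is censored at the last adequate assessment, meaning a BICR response that is neither unknown nor missing. Progression or death after two or more consecutive missed evaluations is also censored. On patients with site but not central confirmation of progression, SAP 4.2.2.2 says: "such patients have the potential to induce bias in the central review due to informative censoring".

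**Arm B disease follow-up.** Protocol Table 2 footnote a describes "Subjects who stop both drugs early because of an adverse event and disease progression has not occurred at that time". Protocol 7.1.2 covers "All subjects enrolled who complete the study treatment (Arm B) or discontinue from study treatment due to reasons other than disease progression".

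**The concern.** The primary endpoint is BICR-assessed PFS, so it depends on scans continuing until BICR calls progression. Two passages allow a patient to leave the scanned phase on the investigator's call alone; a third says scanning goes on. If a site acts on the first two, a patient with unconfirmed investigator progression is censored just when a BICR event is likely to be near. If the share of such patients differs between arms, the hazard ratio is biased. The trial is open-label, so different shares are plausible.

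The feedback conflict makes this worse. A site that is not told the BICR result cannot tell whether the 8.1.1 instruction to keep scanning applies to its patient.

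**Working it through.** **1. Is the looser wording only an Amendment 5.0 rule?** No. Protocol 4.1 attaches the Amendment 5.0 qualifier to its crossover sentences but not to the survival follow-up sentence. SAP 1.2 has the same trigger, and "This SAP is based on version 4.0 of the CSP". SAP version 2.0 is dated 19 December 2023, before the data cut-off of 03 January 2024. The conflict therefore existed while primary-endpoint data were being collected.

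**2. The plan's own figures.** Inputs from Protocol 9.2: 50 events, HR 0.333, 1:1 allocation, nominal two-sided alpha 0.02 at 38 events and 0.044 at 50.
- Lan-DeMets O'Brien-Fleming spending at information fraction 38/50 = 0.76 gives 0.0203 and 0.0440, which match.
- Schoenfeld power = Φ(½√50 × |ln 0.333| − z) with z = 2.014, i.e. Φ(3.888 − 2.014) = 97.0%. Two-look group-sequential power is 97.1%. Both agree with the stated figure of more than 95%. (Freedman's formula would give 93.6%.)

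**3. Effect on the hazard ratio if scanning stops.** Let q be the share of investigator progressions in an arm that BICR does not confirm and that are not scanned again. Those patients leave the risk set without an event, so the arm's event hazard is multiplied by (1 − q):

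expected HR = 0.333 × (1 − qA)/(1 − qB).

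The documents give no q, so the values below are assumptions. The last column is a simulation in which scanning continues and the BICR event follows after a mean of 6 months (also assumed). It uses exponential times, uniform 30-month accrual, cut-off at month 53 and no dropout.

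| qA | qB | HR, scanning stops | HR, scanning continues |
|---|---|---|---|
| 10% | 10% | 0.333 | 0.333 |
| 10% | 20% | 0.333 × 0.90/0.80 = 0.375 | 0.341 |
| 10% | 30% | 0.333 × 0.90/0.70 = 0.43 | 0.350 |
| 20% | 10% | 0.333 × 0.80/0.90 = 0.30 | 0.328 |
| 30% | 10% | 0.333 × 0.70/0.90 = 0.26 | 0.322 |

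The simulated values with scanning stopped agree with the formula (0.333, 0.374, 0.430, 0.298, 0.259). The simulation produces about 61 events by month 53 against the protocol's 50, so it is used here for hazard ratios, not for event counts.

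**4. Partial compliance with 8.1.1.** If half of the unconfirmed patients keep being scanned, and the delay is ignored, 30% and 10% become 15% and 5%. Then 0.333 × 0.85/0.95 = 0.30 and 0.333 × 0.95/0.85 = 0.37. If 80% keep being scanned (6% and 2%), the results are 0.32 and 0.35.

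**5. Deaths.** PFS events include deaths, which step 3 treats as progressions. If 70% of events were progressions (an assumption), 30% and 10% become 21% and 7%: 0.333 × 0.79/0.93 = 0.28 and 0.333 × 0.93/0.79 = 0.39.

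**6. Power.** If 10%, 20% or 30% of the 50 events were lost and not replaced, power at 0.044 would be 95.3%, 92.8% or 89.2%. The analysis is event-driven, so the likelier effects are delay and possible bias.

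**The case against.** The strongest reply is that 8.1.1 is the operative imaging section and already gives the right rule. Protocol 4.1 lists what survival follow-up records; it does not forbid scans. A site that follows 8.1.1 avoids the problem. This stands: the end of imaging at investigator progression is inferred from the content of the phase and the tables, not stated.

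A reader might infer that the SAP has no safeguard. It has several that do not depend on any condition:
- investigator-assessed PFS with HR and CI;
- concordance of progression by arm;
- PFS without censoring for missed evaluations, with a reversed-censoring plot;
- a summary of prematurely censored patients by arm, and of days from censoring to cut-off.

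Only the count of unconfirmed patients and the next-visit imputation depend on an important discrepancy, which is not defined. These analyses can show the problem but cannot restore missing scans.

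Before the final analysis, crossover from Arm B required BICR-confirmed progression (Protocol 6.8). That gave Arm B a reason to keep scanning, which argues against heavy loss there. It does not apply to Arm A, so it does not rule out unequal loss. This is inference, not a documented fact.

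Footnote a might be read as dropping Arm B patients who stop for reasons other than an adverse event. The documents do not support that. The footnote does not say that it is exhaustive. Footnote c schedules evaluations until progression whatever the reason for stopping. Protocol 7.1.1 keeps patients who discontinue on study visits, and 7.1.2 names completers and all other non-progression stops.

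**Conclusion.** The conflict between Protocol 4.1 with SAP 1.2 and Protocol 8.1.1 is real, as is that between SAP 3.2.6 and 8.1.1. The route to informative censoring follows from the SAP's own rules. It is a moderate consistency error, not a design choice.

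The size cannot be computed from the documents. Equal discordance by arm leaves the HR near 0.33. Only unequal rates move it: illustratively 0.26 to 0.43 at 30% versus 10% with no continued scanning, and about 0.30 to 0.37 if half continue. These figures rest on assumed discordance and compliance rates, and the deaths adjustment narrows them further.

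A reader might infer that the primary hazard ratio is biased, or biased in a known direction. The documents support neither: they do not show how many progressions went unconfirmed, which rule sites followed, or that any imaging stopped.

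**What to change.** 1. In Protocol 4.1, 7.1.2, the schedule-of-assessments footnotes and SAP 1.2, state that for the primary analysis scheduled response evaluations, including CT, end at BICR-confirmed progression and survival follow-up starts then. State that investigator-assessed progression applies only after the final analysis. This concerns endpoint follow-up; it takes no view on study treatment.
2. Reconcile SAP 3.2.6 with Protocol 8.1.1 on whether BICR results go back to sites.
3. As a minor consistency edit, align Table 2 footnote a with Protocol 7.1.2.
4. New wording cannot recover scans for an analysis already done: the Synopsis treats the 03 January 2024 cut-off, with 48 BICR events, as the final analysis. So also state which rule sites followed. Report by arm the patients with unconfirmed investigator progression whose imaging stopped. Run the SAP's next-visit event imputation as an unconditional sensitivity analysis.

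The cost is text edits, one table and one sensitivity analysis using a method the SAP already describes. No scan is added beyond those 8.1.1 already required.
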